## Protocol

### Passive Mobile Self-Tracking of Mental Health by Veterans with Serious Mental Illness

NCT 05023252

April 29, 2020

This project studies passive mobile sensing with Veterans in treatment for serious mental illness (SMI). Data are used for self-tracking behaviors and symptoms. While passive mobile sensing has been feasible, acceptable and safe in patients with serious mental illness, these are studied for the first time in VA. Analytics are developed that use passive data to predict behaviors and symptoms. The project has these objectives:

1. Conduct user-centered design of passive mobile self-tracking to support Veterans' management of their mental health.
2. Study the feasibility, acceptability and safety of passive self-tracking of mental health that includes feedback of mental health status to the Veteran.
3. Use mobile sensor and phone utilization data to develop individualized estimates of sociability, activities, and sleep as measured by weekly interviews.
4. Study the predictive value of using data on sociability, activities, and sleep to identify exacerbations of psychiatric symptoms.

The informatics platform will capture an array of passive sensing data off participant's smartphone device to track metrics indicative of behavioral patterns and physiological well-being. These metrics are all passively collected, requiring no active user input, to minimize user burden and ensure maximal user participation in the study. Comparison data will also be collected in the form of weekly assessments conducted by research staff via telephone.

The project will perform statistical analysis on the data to find which short- and long-term features could be correlated with clinical status. These features include both short- and long-term behavioral data, i.e. what an individual has done recently and how their behavior has changed over time. To generate these long-term features, our team will perform time-series analysis on the data and find which parts of participants' daily lives have changed over the course of the study. We will compare these changes to surveys collected at different points throughout the duration of the research study. After generating the relevant features, we use machine learning techniques to study a classifier which predicts whether an individual is in a risk group or not.

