Using multivariate analyses, we study whether quantitative baseline patient characteristics described above are associated with feasibility, acceptability, and safety. Qualitative data from patients 3-month and 9-month interviews are used to evaluate themes related to the feasibility, acceptability and safety of sensing. Qualitative data from post-intervention clinician interviews are used to evaluate themes related to patient engagement, findings, implementation, and resources for sustainability and incorporation into routine practice. Using ATLAS.ti, transcripts of interviews will be coded deductively for major subthemes regarding acceptability, strengths and weaknesses, barriers and facilitators of use, safety, and recommendations about future revisions and implementation efforts. The qualitative findings will be triangulated with findings from the other measure of acceptability and safety to examine whether concordance exists among these measures of the intervention. Should analytic anomalies in the quantitative findings arise, the qualitative data will be explored to illuminate possible explanations for unexpected findings. At 3 and 9 months, 26 individuals should be sufficient to provide data saturation regarding acceptability of the intervention using qualitative data.

Aims 3 & 4. Use mobile sensor and phone utilization data to develop individualized estimates of sociability, activities, and sleep as measured by weekly interview. Study the predictive value of using data on sociability, activities, and sleep to identify exacerbations of psychiatric symptoms.

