Given the reduced number of features, various supervised machine learning algorithms will be used to train prediction models for patient behaviors and symptoms. At the preliminary analysis stage, a set of supervised learning algorithms will be explored to evaluate cross-sectional associations between mobile data features and patient behavioral assessments, with the goal of narrowing down the pool of candidate predictors. First, we will consider random forests. A random forest is a collection of decision trees, each built using a random sample of features, and trained on a bootstrap sample from the original data. Random forests are useful for identifying complex interactions among features due to the use of decision tree learning, while protecting against overfitting by means of bootstrap aggregation. Second, we will consider support vector machines (SVM). SVM is a method of supervised learning which classifies instances into categories by estimating a hyperplane that separates instances belonging to different classes. SVM may be used if the outcomes of interest, behaviors and symptoms, can be meaningfully categorized (e.g., high vs. low). Selected predictors from these approaches will be used in the next step of the model building process that takes into account the temporal correlation and time series nature of mobile data and patient assessments. We will use hidden Markov models to predict patients' current behaviors and symptoms based on current features and past patients' behaviors and symptoms. We view patients' features as observed states, and patients' behaviors and symptoms are hidden states that enjoy the Markov property. We will also use linear or generalized linear mixed effects models to predict patient behavioral assessments using selected features from the preliminary stage, while taking into account within-patient correlation in repeated measurements over time.

Models developed using supervised machine learning methods will be evaluated in terms of out-of-sample predictive performance using leave-one-out cross-validation (LOOCV). For time series modeling, models will be trained on times 1, ..., t-1, and evaluated on time t, for each time t. For cross-sectional modeling, models will be trained on all but patient i, and evaluated on patient i, for each patient i. Performance will be averaged across hold-out times/patients to obtain a LOOCV estimate of

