generalization error. Quadratic loss will be used to evaluate prediction error. The selected model will be the one that minimizes LOOCV mean squared error.

In Aim 4, outcome data are collected weekly for each patient on three scales (psychosis, mania, depression). These scales each have a range of 1 to 7. The primary outcome will be the scale indicating the most severe symptoms in a 2-month window. We will evaluate the association between mobile data features identified in Aim 3 with this primary outcome using a mixed effects model to accommodate within patient data correlation due to repeated measures. Specifically, we will consider feature data from fixed time windows preceding the most severe symptoms. The outcome data distribution will be examined prior to model fitting, and an appropriate link function will be used in the mixed effects model.

Sample size and power considerations: In Aim 3, we extract features of mobile sensor and phone utilization data to estimate behaviors in the domains of sociability, activity, and sleep. The selected features should have a high correlation with behaviors to be a good estimate. Of 100 participants enrolled, assuming 30% attrition, we expect to have complete data on 70 participants (and substantial longitudinal data for a larger group). This sample size will provide over 95% power to detect a correlation of at least 0.50 at the significance level 0.05 using a two-sided test. In Aim 4, our inclusion criteria select for greater than average symptom risk, so we anticipate substantial symptoms. Previous research on 21 patients with SMI for a median of 134 days found that sensing data predicted symptom indicator scores with correlations in the range of 0.5 to 0.8. Given possible confounders, and since our sample may be more heterogeneous than prior research, the correlation in our study is anticipated to be lower than what was reported previously. With 100 enrolled, and assuming 30% attrition, we will have over 85% power to detect correlations of at least 0.35 between predictors of interest and symptoms assessments at the significance level of 0.05 using a two-sided test.

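### The Aim 4 model uses feature windows timed by the observed symptom peak, so it cannot give a false-alarm rate or predictive value for exacerbations, and the planned out-of-sample validation reports only mean squared error

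*Combined protocol and SAP*

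**What the plan says.** The aim is worded as prediction. Objective 4, repeated under Data Analyses for Aims 3 & 4, reads: "Study the predictive value of using data on sociability, activities, and sleep to identify exacerbations of psychiatric symptoms". The overview adds that machine learning will be used to study "a classifier which predicts whether an individual is in a risk group or not".

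The Aim 4 paragraph of Data Analyses is worded as association. On the outcome: "The primary outcome will be the scale indicating the most severe symptoms in a 2-month window". On the analysis: "We will evaluate the association between mobile data features identified in Aim 3 with this primary outcome using a mixed effects model". On the predictors: "we will consider feature data from fixed time windows preceding the most severe symptoms". The power statement for this aim concerns a correlation of at least 0.35.

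Earlier in the same joint section for Aims 3 & 4, the plan does describe prediction of symptoms: "various supervised machine learning algorithms will be used to train prediction models for patient behaviors and symptoms", and "We will use hidden Markov models to predict patients' current behaviors and symptoms based on current features and past patients' behaviors and symptoms". A support vector machine is optional, for use if outcomes can be split meaningfully into high and low. Supervised models are checked by leave-one-out cross-validation, holding out either each patient (cross-sectional models) or each time t after training on times 1 to t-1 (time-series models). The only loss is quadratic, and the selected model is the one with the smallest cross-validated mean squared error.

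**The concern.** An app meant to identify exacerbations has to be judged on two quantities: how many exacerbations it flags, and how many of its flags are wrong. Both need an event definition and both need the ordinary weeks, because that is where false alarms arise. The Aim 4 model has neither. Its outcome is a severity score, and its predictor windows are placed by a peak that is known only once the 2-month window has closed. In use, nobody would know which week is about to be the worst.

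The risk is one of interpretation. A significant Aim 4 coefficient could be read as evidence that passive sensing can flag exacerbations, when the analysis would be compatible with a tool that misses most of them and is wrong most times it fires.

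**Working it through.** **1. The plan's own figure.** Inputs from the sample size paragraph: 100 enrolled, 30% attrition, so n = 100 × 0.70 = 70; two-sided alpha 0.05. With Fisher's z, power = Φ(atanh(r)·√(n−3) − 1.96).

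- Aim 4, r = 0.35: 0.365 × √67 = 2.991; 2.991 − 1.960 = 1.031; power 84.9%. A simulation of the exact test gives 85.3% and the noncentral t gives 86.9%. This agrees with the stated figure of over 85%.
- Aim 3, r = 0.50: 0.549 × √67 = 4.496; 4.496 − 1.960 = 2.536; power 99.4%, consistent with over 95%.

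The power figures stand. They answer whether a correlation differs from zero.

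**2. Objective against analysis.**

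| Needed for Objective 4 | Aim 4 paragraph | Joint Aims 3 & 4 methods |
|---|---|---|
| Definition of exacerbation or risk group | None | None; possible high/low split, no cut-off |
| Predictor window fixed before the outcome is seen | No, placed by the observed peak | Yes for time-series models (train to t−1, test on t) |
| Weeks away from a peak included | No | Yes |
| Out-of-sample assessment | Not mentioned | Leave-one-out by time or by patient |
| AUC, sensitivity, specificity, PPV, calibration | None | None; mean squared error only |

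The methods text supplies much of what the Aim 4 paragraph lacks. No part of the plan supplies the first row or the last.

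**3. What peak-timed windows do to the association.** Assumed, not in the documents: 36 weekly assessments in four 9-week windows, a correlation of 0.35 between one week's feature and the next week's symptoms, lag-1 autocorrelation 0, 0.5 or 0.8, 4,000 simulated patients. Keeping only the week before each window's peak uses 4/36 = 11% of the weeks.

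| Autocorrelation | All-weeks correlation | Peak-window correlation | Mean feature before peak (SD above overall mean) |
|---|---|---|---|
| 0 | 0.35 | 0.23 | 0.51 |
| 0.5 | 0.35 | 0.25 | 0.45 |
| 0.8 | 0.35 | 0.30 | 0.33 |

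The peak-window association therefore estimates something other than the week-to-week relation; under these assumptions it is smaller.

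**4. What r = 0.35 could mean for flagging.** Assumed: feature score X and symptom severity Y bivariate normal over weeks with r = 0.35; event = top share p of Y; flag = top 10% of X. Then PPV = P(X > 1.282, Y > c)/0.10 and sensitivity = P(X > 1.282, Y > c)/p, where c is the upper-p normal quantile.

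| p | Joint probability | PPV | Sensitivity | AUC |
|---|---|---|---|---|
| 5% | 0.0138 | 14% | 28% | 0.71 |
| 10% | 0.0241 | 24% | 24% | 0.69 |
| 20% | 0.0405 | 40% | 20% | 0.67 |

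Per 1,000 weeks at p = 10%, there are 100 events and 100 flags, of which 24 are right and 76 wrong; random flagging would be right for 10. At r = 0.50 the AUC would be 0.79, 0.77 and 0.75.

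**The case against.** The strongest reply is that the Aim 4 paragraph should not be read alone. The section is headed for Aims 3 and 4 together, trains models for symptoms as well as behaviors, includes hidden Markov models for symptoms, allows a high/low classifier, and validates out of sample at every time t or with each patient held out. This stands. A reader might infer that predictive performance is never measured, or that the whole plan offers only an association; the documents do not support either. Prediction error for symptom level is planned, out of sample.

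Two further inferences also fail. The Aim 4 mixed model is not stated to be in-sample; the plan names mixed models as a prediction tool just before describing cross-validation, and the Aim 4 paragraph simply does not refer back to it. Nor is the design case-only: every 2-month window has a maximum, so mild peaks from stable periods enter alongside severe ones.

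The figures in step 4 are also open to challenge. The documents give no exacerbation rate or threshold. The 0.35 comes from a calculation on 70 participants and is a minimum detectable value, not the expected accuracy of a multi-feature model, and applying it to weeks changes the unit. The plan cites correlations of 0.5 to 0.8 from earlier work, though it expects lower here. Finally, the overview's classifier concerns individuals and is not tied to Aim 4, and predictive value need not mean PPV.

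What the reply does not remove: mean squared error for symptom level does not say how many exacerbations are caught or how many flags are false. The support vector machine is conditional and belongs to a preliminary stage for narrowing predictors. The hidden Markov model targets current symptoms and uses past symptoms too, so it does not isolate advance warning from sensor data.

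**Conclusion.** The point holds in a limited form. The Aim 4 analysis, as specified, times its predictors by the outcome and omits weeks away from a peak, so that model cannot produce a false-alarm rate or predictive value. The validation elsewhere in the section could be extended to do so, but at present reports only mean squared error, and the event and the risk group are undefined. It would go too far to say that the plan as a whole cannot address Objective 4: the data and most of the validation framework are already there.

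The size is illustrative. Under step 4's assumptions, a correlation that the trial has about 85% power to detect goes with an AUC of 0.67 to 0.71 and a PPV of 14% to 40%, depending mainly on an event rate that the documents do not give. Under step 3's assumptions, peak timing moves a weekly correlation of 0.35 to between 0.23 and 0.30. Neither range forecasts this trial's results. The change is worth making before analysis; it does not call the sample size into question.

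**What to change.** Amend the Aim 4 paragraph as follows.

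- For every assessed week, use a feature window that closes before that week's interview to predict its BPRS factor scores.
- Have the sponsor prespecify, before analysis, an exacerbation definition based on those scores. Either define the overview's risk group and tie it to an analysis, or remove it.
- Refer explicitly to the existing cross-validation and extend it so that patients are held out for the Aim 4 predictions. Report AUC, sensitivity, specificity, PPV and calibration against a base-rate reference.
- Keep the peak-window mixed-model association as a secondary analysis.

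The cost is SAP wording and some added analysis time. Symptoms are already assessed weekly and sensor data transmitted daily, so no extra data collection is needed. The downside is that the headline result may look less favourable than a correlation.

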### Methods

This study that will enroll patients with mental health diagnoses at risk of symptoms who own a smartphone. Participants will download a smartphone application to their phones which will capture an array of data for a period of nine months. Initially, we conduct focus groups and in-lab usability testing with patients and interviews with clinicians to ensure that development of this functionality is consistent with this VA population. We will conduct 3 focus groups with patients (N=18) and interviews with clinicians (N=10) and make resulting modifications to the app. After these, we conduct in-lab usability testing with 8 patients and make resulting modifications to the app.

Then participants will be recruited and enrolled into the mobile sensing trial where they will download a smartphone application to their phones which will collect an array of data passively for a period of nine months. Participants will receive research assessments from a research assistant at baseline and final follow-up. They will also be asked to complete brief surveys with a research assistant

by phone once a week. A subsample will also complete a semi-structured qualitative interview by phone at 3- months and in person at 9- months. For the duration of each participant's involvement, mobile sensor data are collected. Data are transmitted daily to the server.

For all phases of the study, patients are recruited based on being in treatment for a serious mental illness, being at risk of symptoms, and using a mobile phone. Participants will receive assessments from a research assistant at baseline and follow-up. This baseline and follow-up assessments will be conducted by a research assistant. Patient interviews assess recent medication adherence, housing status, substance abuse, psychiatric symptoms, cognitive deficits associated with SMI, and functioning. In addition, each week, research staff will contact participants by phone, and administer brief assessments of sociability, activity, sleep, and mood and psychotic symptoms. At the conclusion of the study period, the participant will come to the VA to meet with research staff for a final quantitative follow-up interview which includes the same measures from the baseline assessment. At 3 and 9 months, a semi-structured interview is conducted with a subsample by phone to elucidate the feasibility, acceptability and safety of mobile sensing. At the end of the study period, the app will be deleted from the phone, and the participant will be notified that it is no longer functional.

#### Recruitment and screening

A list of potentially eligible participants at the GLA VA will be identified from VA data. We will obtain demographic information, mental health diagnoses, variables determining high risk status (per inclusion criteria), name, last 4 of social security number, address, and telephone number. These data are available through VA Informatics and Computing Infrastructure (VINCI) accessing the Corporate Data Warehouse (CDW), or medical center data systems. We will use an opt-out letter to invite individuals to find out more about the study. If eligible participants do not opt out, they will be contacted by the research team to inquire about study interest. The research team will field calls in response to the letter (both those who want to opt out and those who self-initiate a call for more study information). We will also post flyers at clinics of the Greater Los Angeles VA inviting participation and field calls in response to these.

#### Patient Participant Eligibility

The study involves distinct patient samples: participants in 3 focus groups (n=6 each), participants in an individual in-lab usability trial (n=8), and users of the app for 9 months (n=100). The inclusion and exclusion criteria are the same for all samples, as are the recruitment methods. An individual can participate in one focus group, an in-lab usability trial, and the mobile sensing trial. Furthermore, individuals can participate in the in-lab usability trials or mobile sensing trial and not have participated in the focus groups.

Inclusion criteria: 1) chart diagnosis of SMI, defined as a diagnosis of schizophrenia, schizoaffective disorder, or bipolar disorder, confirmed by the patient's treating psychiatrist; 2) risk for symptoms based on having had, during the past year, psychiatric hospitalization, psychiatric emergency care, lived at a crisis treatment program, or more than 6 outpatient treatment visits; and, 3) ownership of a phone with a data plan.

Exclusion criteria: 1) under age 18. 2) Patient has a conservator/legally authorized representative who makes their medical decisions.

#### Staff participant eligibility

Inclusion criteria: clinicians who are involved in treating individuals with SMI at GLA VA.

Exclusion criteria: none

### Staff Stakeholder Interviews

A purposive sample of 10 clinicians who are involved in treating individuals with SMI at the GLA VA will be interviewed in person before the intervention is implemented and after. These interviews will be conducted after interviewees complete a verbal informed consent process. The baseline interviews will assess acceptability of mobile sensing from a clinician perspective, including usefulness as a tool to improve clinical assessment and care and their recommendations for program refinements. The follow-up interviews will ask about how to reach the appropriate population, reflections on our findings, intention for referrals, implementation issues, and resources needed for sustainability and incorporation into clinical practice. These 30-minute interviews will be digitally recorded and transcribed.

### Patient Participant Eligibility Check

For those interested in participating, additional eligibility criteria will be confirmed by self-report by phone. We will ask the prospective participant if they own a smartphone and help them to determine if it has a data plan. We will confirm their primary psychiatric diagnosis. After confirming eligibility criteria, potential participants will be scheduled to receive further information, confirm the eligibility assessment, and conduct full informed consent. We will tell potential participants to bring their cell phone and a recent cell phone bill to that meeting to confirm phone platform and data plan.

**Participant Consent:** After explaining the study, if the Veteran is interested, research staff will schedule an appointment to review and sign the informed consent form in-person. Research staff will use informed consent procedures validated in individuals with serious mental illness and limited English language proficiency. These involve an iterative process of querying the participant's understanding with a 10-item true/false test on key consent information and providing feedback until an acceptable level of understanding is achieved (no less than 100% correct after no more than 3 tries). It is our experience that almost all (more than 95%) outpatients with serious mental illness can successfully complete this informed consent process. Patients unable to successfully answer all questions on the consent quiz after 3 attempts will not be eligible to enroll.

